2 STUDY DESIGN OVERVIEW

2.1 Overall Study Design

This is a single-dose, multiple-dose, randomized, double-blinded, placebo-controlled, two-staged study in Parkinson's disease subjects with constipation. The study will consist of two stages, each with run-in period and dosing periods and followed by a wash-out period of 2 weeks. Stage 1 will consist of 10 subjects while Stage 2 will consist of 40 subjects to ensure at least 34 evaluable subjects are obtained. During Stage 1, after providing informed consent, subjects will be screened for eligibility. Qualified subjects will proceed through all the dose escalations of ENT-01 starting at 25 mg and ending at 200 mg or at the dose at which s/he experiences a dose limiting toxicity (DLT). Stage 1 is staggered, where the first two subjects will be administered a single dose of 25 mg first. The rest of the subjects will be dosed after the first two subjects have been observed for 72 hours with no safety concerns. The doses to be tested are 25mg, 50mg, 75mg, 100mg, 125mg, 150mg, 175mg and 200mg. Subjects will then be observed off study drug for two weeks during the wash-out period. STDE (Safe and Tolerable dose in all and pro-kinetic Effect in at least some) dose will be identified and carried over to Stage 2.

In Stage 2 under protocol dated 27 July 2017, subjects who signed the informed consent and are eligible will go through a multiple dose escalation (3 dosing days at each dose) period. The dose range is 75 mg up to 175 mg with an increment of 25 mg for next higher dose. Ten subjects will be in the sentinel group and will be dosed first. The dose at which the subject experiences a consistent pro-kinetic effect (spontaneous, complete stool in at least 2/3 consecutive doses) without a DLT will be the dose selected going forward for that subject. This will be the LSTDEi (i.e. consistently clinically effective safe and tolerable dose for that particular individual). After the LSTDEi is established, subjects will continue to take this dose for 2-4 days, followed by randomization on the LSTDEi dose with a 1:1 ratio to ENT-01 or placebo in block sizes of 4 for a 6-day period (period 4). Seven subjects from the ENT-01 group and three subjects from the control group will be in the PK group and have the PK measurement taken. The rest will be in the non-PK group. All the subjects will then enter the wash-out period for two weeks.

The protocol dated 27 July 2017 was amended during the trial. And the protocol amendment was finalized on 02 February 2018. In this amendment, Stage 2 dose range is from 100 mg to 250 mg with an increment 25 mg for next higher dose. It also removed randomization period.

Except for the above changes, there were no other changes from protocol dated 27 July 2017

Table 1: Overall Study Design

Period 1	STAGE 1			STAGE 2A			Period 5
	Period 2.1	Period 2.2	Period 3.1	Period 3.2	Period 4	Period 5	
Run-in sentinel group (Cohort 1)	Single dose escalation sentinel group	Washout	Run-in (Cohort 2)	Identification of prokinetic dose using a 10 subject sentinel group followed by the remaining subjects	1:1 Randomization onto placebo or prokinetic dose	Washout	
2 weeks N=10	3 weeks N=10	2 weeks N=10	2 weeks N=40	≤17days N=40	6 days N=40	2 weeks N=40	

Table 2: Schedule of Assessments of Stage 1

Period	1 Run-In Sentinel 2 wks		2.1 Single Dose 3-8 wks	2.2 Wash-Out 2 wks
	D1	D14	D1	
Consent	X			
Demographics	X			
Inclusion/exclusion	X	X		
Medical history	X			
Physical exam	X		X	X
Vital signs ¹	X		X	X
Rome-IV	X			
Blood chemistry	X		X	X
Hematology	X			
Urinalysis	X			X
Fecal occult blood	X		X	X
EKG	X		X	X
Pregnancy test	X			
Monitoring			X	X
Discontinue medications	X			
Re-start medications				X
Diary entries	X	X	X	X
UPDRS	X		X ⁴	X ²
I-Button ³	X	X	X	
PAC-QOL	X	X	X ⁴	X ²
PAC_SYM	X	X	X ⁴	X ²
RBDQ	X		X ⁴	X ²
NMSQ	X		X ⁴	X ²
PFS-16	X		X ⁴	X ²
UM-PDHQ	X		X ⁴	X ²
BDI	X		X ⁴	X ²
Trail-making A and B	X		X ⁴	X ²

Table 2: Schedule of Assessment of Stage 1

Period	1 Run-In Sentinel 2wks		2.1 Single Dose 3-8 wks	2.2 Wash-Out 2 wks
	D1	D14		
MMSE	X		X ⁴	X ²
Adverse events		X	X	X
PK samples			X ⁵	
Schedule visit days	X			
Administer ENT Dose			X	
Record Medications	X	X	X	X
Daily phone calls to on non-visit days		X	X	X

¹Vital signs taken before dose and 2 hours after dose

²End of period 2

³I-Button placed days 9 of run-in periods and worn continuously through day 5 of wash-out periods.

⁴Surveys taken at last dosing visit

⁵PK samples taken pre-dose and 1, 2, 4, 8 and 24 hours post-dose

Table 3: Schedule of Assessments of Stage 2 under Protocol Dated 27 July 2017

Scheduled Assessments	Period 3.1 Run-In					Period 3.2 Multiple Dose		Period 4 Randomized Treatment			Period 5 Wash-Out	
	Day 1 Visit 1	Days 2-7, 9- 10, 12-13 Calls	Day 8 Call	Day 11 Visit 2	Day 14 Call	Days. 1-13, 15-16 Calls	Day 14 Call	Day 1 Visit 3 ⁶	Days 2-5 Calls	Day 6 Visit 4	Days 1-7 Calls	Day 14 Visit 5
Informed Consent	X											
Inclusion/Exclusion Criteria	X											
Demographics/Medical History	X											
Prior and Con Meds	X											
Complete Physical Exam	X											X
Height	X											
Weight	X			X				X		X		X
Vital Signs ¹	X			X				X		X		X
ECG	X							X				X
Local Labs -Chemistry, Hematology	X							X		X		X
Local Labs - Urinalysis, Serum Pregnancy	X											
Fecal Occult Blood	X							X				X
Randomization								X				
Study Drug Dispense, Accountability, or Collection				X				X		X		
Reminder to Begin Taking Study Drug the Next Morning					X							
Instructions to Discontinue Laxatives and other BM Medication	X											
Instructions to Discontinue Laxatives and other BM medications												X
Stool and Sleep eDiary Instruction/Review	X	X	X	X	X	X	X	X	X	X	X	X
AE Review		X	X	X	X	X	X	X	X	X	X	X
Rome IV questionnaire	X		X									
UPDRS	X							X				X
PAC-QOL and PAC-SYM	X				X		X	X		X		X
Questionnaires- BDI, NMSQ, PFS-16, UM- PDHQ, MMSE, Trail-Making A and B, RBDQ and PDSS	X							X		X		X
Sitzmarks Capsule Distributions ²	X							X				
Reminder to Take Sitzmarks Capsules ³		X							X			
Abdominal X-Ray				X						X		
Dispense I-Button ⁴	X											

Scheduled Assessments	Period 3.1 Run-In					Period 3.2 Multiple Dose		Period 4 Randomized Treatment			Period 5 Wash-Out	
	Day 1 Visit 1	Days 2-7, 9- 10, 12-13 Calls	Day 8 Call	Day 11 Visit 2	Day 14 Call	Days. 1-13, 15-16 Calls	Day 14 Call	Day 1 Visit 3 ⁶	Days 2-5 Calls	Day 6 Visit 4	Days 1-7 Calls	Day 14 Visit 5
PK Draws & LFT ⁵								X		X		
Phone Call		X	X		X	X	X		X		X	

¹ For PK patients, vital signs taken pre-dose and 2 hours after dose. Blood pressure will be taken for all patients twice, first lying down and then after 5 minutes of sitting or standing from the recumbent position. All other vital signs will be measured after the patient has been resting in a sitting position for at least 5 minutes.

²Sitzmark capsules are dispensed to patients at Visit 1 with instructions to take one a day on Days 8, 9, and 10 of the Run-In period for the abdominal X-ray on Day 11. Patients will receive more Sitzmark capsules at Visit 3 with instructions to take one a day on Days 3, 4, and 5 of the Randomized Treatment period for the abdominal X-ray on Day 6.

³Subjects are reminded during the Day 7 call of the Run-In period and Day 2 call of the Randomized Treatment period to begin taking the Sitzmark capsules the following day to prepare for the abdominal X-ray on Day 11 of the Run-In period and Day 6 of the Randomized Treatment period.

⁴Patients will wear an I-Button continuously from Day 8 of the Run-In period to Day 5 of the Wash-Out period except during periods of bathing.

⁵PK samples are taken pre-dose and 1, 2, 4, and 8 hours post-dose. A sample for liver function tests will be taken with the 8-hour post-dose PK draw.

⁶Visit 3 occurs on the day before randomization in non-PK subject

Table 4: Schedule of Events of Stage 2 under Protocol Dated 02 February 2018

Scheduled Assessments	Period 3.1 Run In					Period 3.2 Dose Escalation		Period 4 Fixed Dose		Period 5 Wash Out		
	Day 1 Visit 1 Screening	Days 2-7, 9,10,12,13 Phone Calls	Day 8 Phone Call	Day 11 Visit 2	Day 14 Phone Call	Days 1-13 Phone Calls	Day 14 Phone Call	Days 1-3 Phone Calls	Day 4 Visit 3	Days 1-7 Phone Calls	Day 14 Visit 4	Day 28 FU Call
Informed Consent	X											
Inclusion/Exclusion Criteria	X											
Demographics/Medical History	X											
Concomitant Medications	X	X	X	X	X	X	X	X	X	X	X	
Complete Physical Exam	X											X
Height	X											
Weight	X			X					X		X	
Vital Signs (1)	X			X					X		X	
EKG	X								X		X	
Local Labs: Chemistry*, Hematology*	X								X		X	
Local Labs: Coagulation Panel*	X											
Local Labs: Serum Pregnancy (2a) or FSH (2b)	X											
Urinalysis* (dipstick)	X								X		X	
Urine Pregnancy Test (3)				X					X		X	
Fecal Occult Blood (4)	X								X		X	
Study Drug Dispense, Accountability, Collection				X					X			
Reminder to Begin Taking Study Drug the Next					X							
Instruction to Discontinue Laxatives and Other Restricted Medications (5)	X											
Instruction to Resume Laxatives and Other Restricted Medications										X (6)		
Stool and Sleep Diary Instruction/Review	X	X	X	X	X	X	X	X	X	X	X	
AE Assessment and Review	X	X	X	X	X	X	X	X	X	X	X	X
Rome IV Questionnaire	X		X									
UPDRS	X								X		X	
PAC-QOL and PAC-SYM	X				X		X		X		X	
BDI-II, NMSQ, PFS-16, UM-PDHQ, MMSE, Trail-Making A and B, RBDQ, PDSS	X								X		X	
I-Button	X (7)		X						X (9)	X (10)		

* Refer to Appendix 1 for full list of clinical laboratory assessments

- (1) The first blood pressure and heart rate will be taken after the subject has been in the supine position for at least 5 minutes. The second blood pressure and heart rate reading will be taken while the subject is standing, within 5 minutes of standing from the supine position. All other vital signs (respiration rate and body temperature) will be taken after the subject has been sitting or standing for 5 minutes.
- (2) (2a) For women of child-bearing potential and (2b) For post-menopausal women less than 60 years of age.
- (3) For women of child-bearing potential, done on site with urine pregnancy kit provided
- (4) Subjects will be provided a home testing kit with instructions; to be used at home on the first bowel movement following the visit, and results to be given to the study coordinator at subsequent phone call visit.
- (5) Subjects will be instructed to discontinue all laxatives, bulking agents, softeners and suppositories as well as clonazepam, opiates, etc. as specified in the protocol. Proton pump inhibitors and antacids may be continued until the end of the Run-In Period.
- (6) Subjects will be instructed to resume use of their regular regimen laxatives, bulking agents, softeners, proton pump inhibitors, and antacids after week 1 of wash out.
- (7) Dispense I-Button
- (8) Instruct subjects to begin wearing the I-Button
- (9) Instruct subjects to stop wearing the I-Button at the end of Day 5 of Wash Out
- (10) Collect I Button

2.2 Sample Size/ Power Calculation

No formal sample size calculation was performed for Stage 1. The number of subjects is based on feasibility and is considered sufficient to meet the objectives of the study.

For Stage 2, assuming the highest proportion of spontaneous resolution of constipation with no treatment to be 0.10, 34 evaluable subjects who have measurements at both baseline and at the end of the fixed dose period will provide 80% power to detect the difference between 0.10 (proportion expected if patients are not treated), p_0 , and an ENT-01 proportion, p_E , of 0.29. Assuming a drop-out rate of 15%, a total of 40 subjects will ensure at least 34 evaluable subjects will be obtained.

2.3 Randomization and Blinding

No randomization is performed for Stage 1.

During randomization period of Stage 2 under the protocol dated 27 July 2017, subjects will be randomly allocated in equal proportion (1:1) to 1 of 2 double-blind treatment groups:

- ENT-01 – Patients will remain at dose level taken in period 3.2 of Stage 2
- Placebo – Patients will be switched to the same number of placebo tablets as the dose level taken in period 3.2 of Stage 2

3 STUDY OBJECTIVES

3.1 Objectives for Stage 1

3.1.1 Primary Objective

To investigate the safety and tolerability of single oral doses of ENT-01 in patients with Parkinson's disease related constipation.

3.1.2 Secondary Objective

To evaluate the pharmacokinetic (PK) characteristics of single oral doses of ENT-01 in patients with Parkinson's disease and constipation.

3.1.3 Exploratory Objective

To determine the pharmacodynamic (PD) characteristics of ENT-01 in patients with Parkinson's disease related constipation.

3.2 Objectives for Stage 2

3.2.1 Primary Objectives

- To determine the Safety, Tolerability of repeated oral doses of ENT-01 in patients with Parkinson's disease related constipation.
- To determine the PK and PD characteristics of repeated oral doses of ENT-01 in patients with Parkinson's disease related constipation.

3.2.2 Exploratory Objective

- To determine the effect of study drug on Quality of Life Measures including sleep, temperature, memory, energy, mood, fatigue, hallucinations, memory and executive function in patients with Parkinson's disease related constipation.

4 STUDY ENDPOINTS AND EVALUATIONS

4.1 Pharmacokinetic Parameters

4.1.1 Pharmacokinetic Parameters for Stage 1

The following PK parameters will be determined where possible:

Parameter	Definition
C_{\max}	Maximum or peak measured plasma concentration
C_{\min}	Minimum or trough measured plasma concentration
T_{\max}	Time of maximum or peak measured plasma concentration
$t_{1/2}$	Apparent terminal elimination half-life; calculated as $\ln(2)/\lambda_z$.
AUC_{0-24}	The number of data points included in the regression will be determined by visual inspection, but a minimum of three data points in the terminal phase, excluding C_{\max} , will be required to estimate λ_z . Area under the concentration versus time curve from time 0 to the concentration at 24 hours; calculated using linear trapezoid rule
CL/F	Clearance defined as: Dose/ AUC_{0-24}
λ_z	Apparent terminal rate constant

Additional pharmacokinetic parameters may be determined where appropriate.

4.1.2 Pharmacokinetic Parameters for Stage 2

Pharmacokinetic parameters will not be calculated.

4.2 Safety Evaluations

The safety evaluations for both stages include:

- Treatment emergent adverse events (TEAEs)
- Clinical laboratory assessments
- Vital signs
- Physical examination findings
- Electrocardiogram

4.3 Tolerability Evaluations

Tolerability will be measured by the following DLT endpoints: Dose Limiting Toxicity (DLT) will be the dose which induces repeated vomiting, diarrhea, abdominal pain or symptomatic postural hypotension within 24 hours of dosing. It is defined using the Common Terminology Criteria for Adverse Events (CTCAE) as:

- Recurrent vomiting: 3-5 episodes of vomiting within 24 hours of taking ENT-01 (i.e., 3-5 episodes of Grade 2 vomiting)

- Recurrent diarrhea: 4-6 episodes of diarrhea within 24 hours of taking ENT-01 (will be recoded as a Grade 2 diarrhea)
- Moderate Abdominal pain that limits instrumental activities of daily living within 24 hours of taking ENT-01 (Grade 2 AE)
- postural hypotension including Moderate dizziness, lightheadedness or fainting upon rising from lying to sitting or standing and severe enough to require medical intervention within 24 hours of taking ENT-01 (Grade 2 AE) or either a systolic blood pressure less than 80mmHg or diastolic blood pressure less than 40mm Hg

In addition, the following will also be considered dose limiting toxicity for the purpose of analyses:

- Elevation of LFTs > 3 times the upper limit of normal (ULN)
- A reduction of body weight of 10% or more

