2 OBJECTIVES

The purpose of this study is to evaluate the safety, tolerability, pharmacokinetics and pharmacodynamics of orally administered ENT-01 at doses ranging from 25mg to 200mg in patients with constipation secondary to Parkinson's disease. Dosing will be individually titrated to tolerability and effect. A second objective of the study is to determine the effect of orally administered ENT-01 on gastric emptying and colonic motility. A third objective of the study is to collect information relating to sleep and other non-motor symptoms of PD.

2.1 Stage 1

Primary objective:

The primary objective of the Stage 1 study is to determine the safety and tolerability of a single oral dose of ENT-01 in patients with PD and constipation. The dose will be titrated to tolerability, starting at 25mg daily and increasing up to 200mg daily.

10 patients will be enrolled in the study for 7-12 weeks.

Safety end-point will be:

Adverse events as measured by patient report, vital signs, clinical chemistry, and EKG Tolerability end-points (referred to as the dose-limiting tolerability (DLT)):

- Recurrent vomiting defined as 3-5 episodes of vomiting within 24 hours of taking drug
- Recurrent diarrhea defined as 4-6 episodes of diarrhea within 24 hours of taking drug
- Abdominal pain defined as moderate pain that limits instrumental activities of daily living (ADL) (e.g., preparing meals, shopping for groceries or clothes, using the telephone, managing money, etc.) within 24 hours of taking drug
- Postural hypotension defined as dizziness/lightheadedness or fainting on rising from lying
 to sitting or standing that limits instrumental ADL and severe enough to indicate nonurgent medical intervention within 24 hours of taking drug.
- A fall in systolic blood pressure to <80mm Hg upon rising from lying to sitting or standing
- A fall in diastolic blood pressure to <40mm Hg upon rising from lying to sitting or standing
- Elevation of LFTs > 3 times the upper limit of normal (ULN)
- A reduction of body weight of 10% or more

Secondary objective:

The secondary objective of the Stage 1 study is to evaluate the Pharmacokinetic (PK) characteristics of a single oral dose of ENT-01 in patients with PD and constipation.

Pharmacokinetics:

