MTD: Maximum Tolerated Dose **ID: Intolerant Dose** No prokinetic response MTD ID Day10 Day13 Subject Day 1 Day4 Day7 Day16 Day19 Day22 Day 25 25mg 50mg 100mg 75mg >125mg 150mg 175mg 2 25mg 50mg 75mg 100mg 125mg 150mg 175mg 200mg Stage 1 Period 2.1 3 50mg 75mg 100mg 125mg 150mg 175mg 25mg (COHORT 1) 4 25mg 50mg 75mg 100mg 125mg 150mg Single dose 125mg 5 25mg 50mg 100mg 150mg 75mg 175mg 200mg safety, 50mg 100mg 125mg 6 75mg 25mg tolerability and 50mg 100mg 7 25mg 75mg 125mg 150mg 175mg identification of 8 25mg 50mg 75mg 100mg 125mg 150mg prokinetic dose 50mg 100mg 125mg 150mg 25mg 75mg → 175mg 200mg 10 25mg 50mg 75mg 100mg 125mg 150mg 175mg 200mg STDE DOSE in this example is 75 mg, that being the lowest dose that is safe and tolerable in all subjects and has a prokinetic effect in at least some

Schematic for Stage 1, Period 2.1: Hypothetical dosing regimens

Pharmacokinetics: Timed blood samples (5.0 mL) will be collected into Li-Heparin treated tubes for analysis of ENT-01 plasma concentrations. Plasma samples will be obtained for pharmacokinetics before dose administration and at 1, 2, 4, 8, and 24 hours.

Once collected, PK samples will be stored in a -20°C or -70°C freezer until time of shipment. Labels and appropriate shipping materials will be provided to sites. The concentration of study drug will be determined from the plasma samples using a validated analytical method. Details of the method validation and sample analysis will be included with the final clinical study report.

Individual stopping criteria:

The complete panel of Blood Chemistries described in Appendix 1 are to be drawn 24 hours after each dose. Results will be reviewed the evening before the following dose. In addition, any patient with at least 1 DLT endpoint (see **Section 9.8**), or with another non-DLT gastrointestinal AE > grade 3 that is at least possibly attributable to ENT-01, or elevated AST, ALT, or total bilirubin > 3x ULN or a reduction of body weight of 10% or more from baseline will be terminated. ENT-01 has very little systemic absorption, and hence adverse events are expected to be within the gastrointestinal system.

Refer to Section 9.12 for Adverse Event Grading and to Section 9.8 for DLT Endpoint

Criteria.

Go/No-go decision:

Safety: We are assuming that no more than 1 patient out of ten (10%) will have an adverse event

of grade 4 or 5 that is at least possibly related to ENT-01 in dose levels thought to be below

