9.7 CTCAE Definitions of Dose Limiting Adverse Events

Adverse event	Grade 1	Grade 2	Grade 3	Grade 4	Grade 5
Diarrhea (watery stool)	Increase of <4 stools a day over baseline	Increase of 4-6 stools a day over baseline	Increase of >7 stools a day; incontinence; hospitalization indicated	Life threatening complications; urgent intervention indicated	Death
Vomiting	1-2 episodes per 24 hrs	3-5 episodes per 24 hrs	6 or more episodes in 24 hrs; tube feeding, TPN or hospitalization indicated	Life- threatening consequences; urgent intervention indicated	Death
Abdominal pain	Mild pain	Moderate pain; limiting instrumental ¹ ADL	Severe pain; limiting self- care ADL ²	-	-
Postural hypotension ³	Mild, transient lightheadedness or dizziness	Moderate lightheadedness, dizziness or	Severe lightheadedness, dizziness or	Life- threatening and urgent	Death

upon rising	fainting upon	fainting upon	intervention
from lying or	rising from	rising from	indicated
sitting position	lying or sitting	lying or sitting	
that does not	position that	position that	
interfere with	limits	limits self-care	
ADL	instrumental	ADL; Medical	
	ADL; Non-	intervention or	
	urgent medical	hospitalization	
	intervention	indicated	
	indicated		

Preparing meals, shopping for groceries or clothes, using the telephone, managing money, etc.

9.8 Criteria for DLT Endpoints:

Recurrent vomiting: 3-5 episodes of vomiting within 24 hours of taking ENT-01 (Grade 2 AE)

Recurrent diarrhea: 4-6 episodes of diarrhea within 24 hours of taking ENT-01 (Grade 2 AE)

Abdominal pain: Moderate pain that limits instrumental activities of daily living within 24 hours of taking ENT-01 (Grade 2 AE)

Postural hypotension: Moderate dizziness, lightheadedness or fainting upon rising from lying to sitting or standing and severe enough to require medical intervention within 24 hours of taking ENT-01 (Grade 2 AE) or either a systolic blood pressure less than 80mmHg or diastolic blood pressure less than 40mm Hg.

9.9 **Pre-Existing Medical Conditions**

All subjects enrolled in the study will have Parkinson's disease. Specific pre-existing medical conditions that will be excluded are listed in patient exclusion criteria.

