10.1 Sample Size/Power Considerations

10.1.1 Stage 1

There will be 10 patients enrolled in Stage 1. Two patients will be started on the 25mg dose. If no DLTs are observed, they will be escalated to the next dose and the remaining 8 patients will be started at 25mg. Each dose level will be a single dose and patients will be observed for three days before being given the next higher single dose. It is intended that each patient receive a single dose of each of the levels: 25mg, 50mg, 75mg, 100mg, 125mg, 150mg, 175mg and 200mg. However, if a patient experiences a DLT, they will not be further escalated.

A DLT is defined in Section **9.8** using the Common Terminology Criteria for Adverse Events (CTCAE), as a grade 2 vomiting within 24 hours of taking ENT-01 grade 2 diarrhea within 24 hours of taking ENT-01, grade 2 abdominal pain within 24 hours of taking ENT-01, grade 2 postural hypotension within 24 hours of taking ENT-01. Additionally, an LFT elevation > 3xULN within 24 hours of taking ENT or any gastrointestinal AE > grade 3 within 24 hours of taking ENT-01 that is at least possibly attributable to ENT-01 will be considered dose-limiting toxicity for the purpose of analyses.

There is no power calculation for the Stage 1 portion because it is merely trying to determine whether ENT-01 is safe and tolerable for these levels. The PK analyses will be descriptive and are meant to understand how ENT-01 is metabolized.

10.1.2 Stage 2

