5 PLANNED ANALYSES

5.1 Changes from planned analyses in the Protocol

There are no changes from planned Analyses in the Protocol.

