7.8.6 Analysis of Tolerability Data

Stage 1 and up to end of fixed dosing period in Stage 2

Tolerability will be measured by DLT endpoints defined in Section 4.3.

The frequency of each tolerability endpoints including recurrent vomiting, recurrent diarrhea, abdominal pain and postural hypertension, and etc. will be summarized by dose (Stage 1) or for treatment period (Stage 2). Percentages will be based on the number of subjects in each dose level (Stage 1) or the number of subjects (Stage 2) in the safety population.

Randomization period in Stage 2

Additionally, the above summaries will be provided during the randomization period by treatment for randomized population.

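### SAP 4.3 defines the gastrointestinal dose-limiting events as closed Grade 2 bands, so a stand-alone more severe event is not counted; SAP 7.8.1 also leaves out the 25 and 50 mg Stage 1 dose levels

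*SAP*

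**What the plan says.** Protocol 2.1 gives the Stage 1 tolerability end-points, among them "Recurrent vomiting defined as 3-5 episodes of vomiting within 24 hours of taking drug". Protocol 9.8 repeats the band with its grade: "Recurrent vomiting: 3-5 episodes of vomiting within 24 hours of taking ENT-01 (Grade 2 AE". Diarrhea is set at 4-6 episodes, and abdominal pain at the moderate level that limits instrumental activities of daily living. The grading table in protocol 9.7 puts the next step for vomiting in Grade 3: "6 or more episodes in 24 hrs; tube feeding, TPN or hospitalization indicated". Severe pain is also Grade 3 there.

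SAP 4.3 takes these bands over and adds a gloss on the vomiting criterion: "Recurrent vomiting: 3-5 episodes of vomiting within 24 hours of taking ENT-01 (i.e., 3-5 episodes of Grade 2 vomiting". The postural criterion has two limbs joined by an or: moderate symptoms needing medical intervention (labelled Grade 2), or a blood pressure below 80 systolic or 40 diastolic. Two further items are added for the analyses: liver tests above 3 times the upper limit of normal, and weight loss of 10% or more.

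SAP 7.8.6 ties the tables to that section: "Tolerability will be measured by DLT endpoints defined in Section 4.3".

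Protocol 10.1.1 has one more item, which SAP 4.3 does not carry over: "any gastrointestinal AE > grade 3 within 24 hours of taking ENT-01 that is at least possibly attributable to ENT-01 will be considered dose-limiting toxicity". SAP section 1 says that the SAP takes precedence over the protocol's statistical section.

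SAP 7.8.1 gives the Stage 1 dose levels for adverse event summaries as 75 mg up to 200 mg. SAP 2.1 lists eight Stage 1 doses starting at 25 mg.

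**The concern.** Tolerability is half of the Stage 1 primary objective, and the DLT frequency by dose is how it is measured. Protocol 1.3 expects the main adverse events to be gastrointestinal, so the definitions in question cover the expected toxicity. A tolerability count should not fall as severity rises. With a ceiling on each gastrointestinal criterion and no clause for worse events, the SAP's rule can do that: five vomits are a DLT and six are not.

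The gloss on the vomiting criterion adds a second uncertainty. Grade 2 vomiting is already 3-5 episodes, so 3-5 episodes of Grade 2 vomiting could be programmed as several Grade 2 events. Protocol 9.8 has no such wording.

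The missing 25 and 50 mg levels matter for a simpler reason. Every Stage 1 patient is meant to start at 25 mg, and a by-dose safety table that begins at 75 mg omits the first two steps of the escalation.

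**Working it through.** The plan gives no figure of its own here, so there is nothing to reproduce. The check applies the written definitions, then sizes the result.

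**1. SAP 4.3 as written** (k = episodes within 24 hours of dosing)

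| Criterion | Rule | Counted | Not counted |
|---|---|---|---|
| Vomiting | 3 ≤ k ≤ 5 | 3, 4, 5 | 6 or more |
| Diarrhea | 4 ≤ k ≤ 6 | 4, 5, 6 | 7 or more |
| Abdominal pain | moderate, Grade 2 | moderate | severe |
| Postural, symptom limb | moderate, Grade 2 | moderate, needing intervention | severe, if blood pressure stays above the limits |
| Postural, blood pressure limb | <80 or <40 mmHg | all below the limit | none |
| Liver tests | >3 × upper limit | all above | none |
| Weight loss | ≥10% | all above | none |

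Of the six criteria, three are closed at the top with no open limb (vomiting, diarrhea, pain). One has a closed symptom limb beside an open blood pressure limb (postural). Two are open (liver tests, weight).

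Protocol 9.7 grades diarrhea by the increase in stools over baseline, with Grade 3 above 7. Seven episodes need not be Grade 3, but they are outside the SAP band either way.

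A patient with a more severe event is still counted if any other criterion is met: another gastrointestinal band, either postural limb, liver tests or weight. The gap therefore needs a severe event that stands alone.

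**2. Would the protocol 10.1.1 clause close the gap?**

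- As printed, above Grade 3 means Grade 4-5. It covers Grade 3 for 0 of the 3 closed gastrointestinal criteria.
- Protocol 9.7 defines Grade 4-5 for vomiting and diarrhea but not for abdominal pain, so the clause covers Grade 4-5 for 2 of the 3.
- If Grade 3 or higher was intended, attributable Grade 3 events would be covered.
- SAP 4.3 omits the clause, so under the SAP a stand-alone Grade 3 gastrointestinal event is left out on either reading.

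**3. Size.** SAP 7.8.6 uses as denominator the patients at each dose in Stage 1 and the Safety population in Stage 2. One uncounted patient lowers the DLT frequency by 1/n:

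- Stage 1, dose given to all 10: 1/10 = 10.0 percentage points.
- Stage 1, dose reached by 9 or by 8: 1/9 = 11.1, 1/8 = 12.5. These are illustrations; escalation stops at a DLT, so fewer than 8 may reach the top doses.
- Stage 2, all 40 dosed: 1/40 = 2.5 points.
- No such event: 0.

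The documents give no expected rate for such events, so no expected loss can be computed.

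**4. Stage 1 dose levels.** Tested: (200 − 25)/25 + 1 = 8. In the SAP 7.8.1 range: (200 − 75)/25 + 1 = 6. Left out: 8 − 6 = 2 (25 and 50 mg).

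**The case against.** The strongest reply is that the ceiling was never meant. The sentence that introduces the SAP 4.3 list speaks of repeated vomiting, diarrhea and pain with no upper limit, the protocol's description of Period 2.1 does the same, and the bands simply restate the Grade 2 row of the grading table. A patient who vomits six times has passed three. That is very likely the intent, and it is why the fix is a clarification. It does not settle how the table will be programmed, because SAP 4.3 goes on to say that the DLT is defined by the listed items, and SAP 7.8.6 points to those items alone.

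Three stronger readings are tempting, and the documents do not support them.

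- A reader might infer that severe events disappear from the report. They do not: SAP 7.8.1 tabulates adverse events by maximum grade and separately for Grade 3 or higher, and lists them. Events at 25 and 50 mg likewise remain in the overall summary and the listings, and the DLT table in SAP 7.8.6 is not limited to 75 mg and above. No hypothesis test uses the DLT row.
- A reader might infer that the SAP created the gap by silently dropping the protocol 10.1.1 clause, given that SAP 5.1 says "There are no changes from planned Analyses in the Protocol". As printed, that clause would not have covered Grade 3, and the protocol's stopping rule applies the same cut to a "non-DLT gastrointestinal AE > grade 3 that is at least possibly attributable to ENT-01". SAP 4.3 also follows the list in protocol 2.1, which has no such clause. The two protocol lists differ and the SAP followed one of them, so the undeclared omission is a minor point.
- A reader might infer that a patient with Grade 3 vomiting would go on escalating. The individual stopping rule does refer to protocol 9.8, but protocol 4.5 allows withdrawal on the medical monitor's review or the investigator's judgment.

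**Conclusion.** The definition is wrong as written, with a limited effect. If SAP 4.3 is applied literally, a patient whose only qualifying event is more severe than the band is left out of the DLT frequency, while a patient with a milder event is counted. Each such patient costs one count: 10 points at a Stage 1 dose given to all 10, more where fewer are dosed, and 2.5 points in Stage 2 if all 40 are dosed. The conclusion assumes that the programmer follows the listed bands rather than the open introductory sentence, and that at least one such event occurs with no other criterion met. If either fails, the DLT row is right.

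The Stage 1 range in SAP 7.8.1 is a separate slip that affects only the dose-specific adverse event breakdown at 25 and 50 mg.

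**What to change.** In SAP 4.3, state the three gastrointestinal criteria and the postural symptom limb as Grade 2 or higher within 24 hours of dosing: at least 3 vomiting episodes, at least 4 diarrhea episodes, and at least moderate pain limiting instrumental activities of daily living. Delete the parenthesis that follows the vomiting criterion. In SAP 7.8.1, give the Stage 1 dose levels as 25 mg to 200 mg.

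SAP 5.2 provides for Stage 1 to be analysed when its data are complete. If that has been done, declare the DLT clarification in SAP section 9 as made after those data were seen.

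The cost is a few words in two sections and the matching table programs. The downside is that slightly more DLTs may be reported. Once Grade 2 or higher is stated, restoring the protocol 10.1.1 clause is optional; if it is restored, the sponsor should confirm whether it means Grade 3 or higher, or Grade 4-5. Aligning protocol 9.8 is also optional, and would need an amendment because that section drives individual stopping.
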